3.4 Derived Data and Data Sets

3.4.1 Rules for incomplete data

Missing data will not be replaced.

3.4.2 Rules for efficacy

None.

 3.4.3 Rules for adverse events

Seriousness: 0 ≈ 'no', 1 ≈ 'yes'.

Attribution of the AE to the PowerSpiral Device

A frequency table will be presented showing the the information on attribution of the AE to the PowerSpiral device using the categorization given on the CRFs:

1 ≈ 'not related', 2 ≈ 'unlikely', 3 ≈ 'possible', 4 ≈ 'probable', 5 ≈ 'causal relationship'.
 Moreover, this categorization will be used in data listings.

3.4.4 Rules for laboratory data

Not applicable.

3.4.5 Rules for vital signs

Not applicable.

3.4.6 Rules for physical examination

Not applicable.

3.4.7 Other rules

None.

3.5 Demography, Medical History, Concomitant Medication, Study Procedures

Descriptive statistics (n, mean, standard deviation, median, 25th and 75th percentiles, minimum and maximum) will be calculated for quantitative variables; frequency counts by category will be given for qualitative variables. Confidence intervals will be given where appropriate. If not stated otherwise, these intervals will be two sided in each case and provide 95% confidence. Individual listings will be provided for each parameter examined in this study.

In addition, information on the intervention will be presented as follows:

- Number of patients in whom a complete intervention was planned.
- Number of patients by number of interventions
- Number of patients with complete and incomplete interventions

Intervention

- Were all interventions successfully completed?
- Type of intervention

Intervention time

- Descriptive statistics

Perception of investigator

- Handling of PowerSpiral vs. BAE (worse, similar, better)

Type of sedation

- number of patients with general anaesthesia and sedation

Concomitant medication and medical history will be listed only (if no codes are available).

3.6 Efficacy Analysis

The following efficacy analyses will be performed based on the cITT population and on the ITT population as sensitivity analysis:

- The anatomical success rate (number of cases in which the suspected anatomical region is reached compared to all attempts) will be computed alongside with its 95% Clopper-Pearson confidence interval.
- The therapeutic yield (percentage of patients with any endoscopic intervention/therapy with exception of biopsies) will be presented alongside its 95% Clopper-Pearson confidence interval.
- The total procedure time (period in minutes needed to complete the procedure) will be summarized descriptively.
- The total therapeutic intervention time will be summarized descriptively.
- The total small bowel enteroscopy rate (number of complete evaluations of the small bowel divided by all attempts to reach the small bowel) will be computed alongside its 95% Clopper-Pearson confidence intervals.
- The outcomes for the items in the user feedback for the judgement of handling characteristics and other aspects will be tabulated in frequency tables.
- Diagnostic Yield (i.e. diagnosis, that explains findings from previous imaging or establishes a new diagnosis, that could explain clinical symptoms, that indicated PSE)
 - Diagnostic Yield is defined as the difference of proportion of patients for which a diagnosis was made and the proportion of patients with prior positive imaging (VKE, MRI, other)

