Endpoints	
 • Diagnostic Yield: Defined as the percentage of procedures that either confirmed a diagnosis from previous studies, or established a new definitive diagnosis at the anatomical location identified in previous studies or findings that could explain the clinical symptoms • Therapeutic Yield: Defined as the percentage of patients with any endoscopic intervention / therapy with the exception of biopsies • Total procedure time: (starting with oral /anal insertion until final withdrawal of the device) • Total therapeutic intervention time • Total small bowel enteroscopy rate: Defined as complete evaluation of the small bowel either with a single approach or combined anterograde and retrograde approach (if complete small bowel enteroscopy is intended anyway) • Endoscopic success rate • Safety: Incidence (% of subjects) and frequency (no. of subjects) with device or procedure related Serious Adverse Events (SAEs) and Device Deficiencies (DD) observed during/after the procedure • User feedback and assessment of handling characteristics of the device
Study Design	International, multicenter, open label, non-randomized, prospective, observational study.
Sample Size	260 subjects will be enrolled into this registry including an expected rate of 5% of losses-to-follow-up during study conduct. The first 5 procedures for each investigator will be performed to get used to the device. Data on these “learning curve” procedures will be captured and analyzed separately. The dataset for final analysis (e.g. procedure time, rate of SAEs etc.) will include 260 cases from procedure #6 onwards in order to account for a learning curve effect. The sponsor plans to activate 12 sites with one or two investigators at each site. Each site shall enroll up to 22 subjects (notwithstanding the learning curve cases) to allow for the same quota per site. Overall approximately 335 subjects will be enrolled (including cases for the learning curve).

Clinical Investigation Plan

CIP Reference No.:2018-GI (OEKG) -01. The **SAMISEN** study - Final Version 02 - Date 23th April 2019

Timelines	Study Start (Enrollment of First Patient) is planned for May/June2019. Enrollment period: 1 year (until May/June 2020). Study closure: Q2/2020.

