3.1.2 Randomization and Blinding or Assignment of Investigational Device

SAMISEN is designed as a prospective single-arm trial without control group or randomization. All subjects enrolled will undergo at least one procedure with the Motorized Spiral Endoscope (PowerSpiral). There may be a second (optional) procedure depending on investigator's discretion usually because the region of interest could not be reached during the first endoscopy. Subsequent endoscopic procedures are often characterized by a switch in direction (a first antegrade route may be followed by a second retrograde approach or vice versa). From a study perspective and because only part of the subjects will receive a second procedure this additional procedure is called "optional" to indicate that it is not required by protocol but will only be performed if considered necessary by the treating investigator.

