3.1.3 Variables in the Clinical Investigation

It is a prospective and observational Registry without any additional procedure beyond clinical practice. The small-bowel enteroscopy has to be performed according the medical standard. Serious Adverse Events (SAE) and Device Deficiencies (DD) must be documented.

The main safety endpoint is a combined one, capturing all SAEs / DDs captured during the study period. The definition is:

- **Safety:** Incidence (% of subjects) and frequency (no. of subjects) of device or procedure related Serious Adverse Events (SAEs) and Device Deficiencies (DD) observed during/after the procedure.

As main efficacy endpoint we will determine in how many cases the suspected anatomical target lesion can be reached. The definition is:

- **Diagnostic Yield:** Defined as the percentage of procedures that either confirmed a diagnosis from previous studies, or established a new definitive diagnosis at the anatomical location identified in previous studies or findings that could explain the clinical symptoms (Sethi et al. 2014; Prachayakul et al. 2013; Lenz, Roggel, and Domagk 2013; Sanaka et al. 2012).

Clinical Investigation Plan

CIP Reference No.:2018-GI (OEKG) -01. The **SAMISEN** study - Final Version 02 - Date 23th April 2019

Further efficacy endpoints cover performance aspects of the device. The definitions are:

- **Therapeutic Yield:** Defined as the percentage of patients with any endoscopic intervention / therapy with the exception of biopsies. (Sethi et al. 2014; Prachayakul et al. 2013; Sanaka et al. 2012).
- **Total procedure time:** the time from oral (anal) insertion until withdrawal of the device.
- **Total therapeutic intervention time:** The part of the procedure dedicated to therapeutic maneuvers (biopsies will not be considered here).
- **Total small bowel enteroscopy rate:** Defined as complete evaluation of the small bowel either with a single approach or combined anterograde and retrograde approach (if complete small bowel enteroscopy is intended anyway (Committee et al. 2015; Gerson et al. 2015).
- **User feedback** and judgment of handling characteristics and other aspects.

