- Discontinuation of Anticoagulant therapy prior / during the procedure
- Provide information about the planned small-bowel enteroscopy
 - Main indication for the planned small- bowel enteroscopy procedure.
 - Select if a capsule endoscopy, CT/MRT enteroclysm or another imaging technique was performed previously.
 - Describe if there were any positive findings during the previous diagnostic workup (e.g. if a bleeding was detected).
- Describe the initially planned PowerSpiral approach
 - Is a total enteroscopy of the small-bowel planned?
 - Start with antegrade procedure and add a retrograde one if unsuccessful or incomplete *or*
 - Start with retrograde procedure and add an antegrade one if the initial procedure is unsuccessful or incomplete *or*
 - Perform a combined antegrade and retrograde examination during a single session.

At visit V2 and V3 (optional):

- At this visit the PowerSpiral enteroscopy will be performed.
- Enter the date and name of the responsible investigator who performs the enteroscopy.
- Enter the total procedure time (“scope-in, scope-out”) measured from initial enteroscope introduction through the bite block to final enteroscope withdrawal through the bite block (minutes) (for antegrade approach) or crossing the linea dentata of the anus in case of a retrograde approach.
- Provide information about the kind of staff and number persons needed for this enteroscopy.
- Select if an antegrade, retrograde or combined enteroscopy was performed.
- Select if a general anesthesia or sedation is used.
- Select which part of the small-bowel was reached.
- Answer if the findings of the previous imaging examinations were confirmed or not.

Clinical Investigation Plan

CIP Reference No.:2018-GI (OEKG) -01. The **SAMISEN** study - Final Version 02 - Date 23th April 2019

- Answer if there was any therapeutic intervention performed. If yes please specify in the free text section.
- Enter the time needed for any therapeutic intervention. If several slots for therapeutic interventions occurred, please add the time needed for each therapeutic slot and enter the total duration in minutes.
- Answer if any Serious Adverse Events occurred during the enteroscopy procedure.
- Document the final diagnosis after the enteroscopy
- Answer the following questions:
 - Was the therapeutic intervention successful and were all planned therapeutic aim(s) achieved?
 - Was the initial therapeutic management plan modified during the procedure?

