4.1.2 Efficacy evaluation

The efficacy endpoints are defined as follows:

- **Reaching the anatomical region of interest:** The rate of successfully reaching the suspected anatomical target region (either by antegrade or by retrograde route) compared to all attempts represents the **anatomical success rate**.
- **Therapeutic Yield:** Defined as the percentage of patients with any endoscopic intervention / therapy with the exception of biopsies. (Sethi et al. 2014; Prachayakul et al. 2013; Sanaka et al. 2012).
- **Total procedure time.**
- **Total therapeutic intervention time:** period in min dedicated to therapeutic intervention(s).
- **Total small bowel enteroscopy rate:** Defined as complete evaluation of the small bowel either with a single approach or combined anterograde and retrograde approach (if complete small bowel enteroscopy is intended anyway (Committee et al. 2015; Gerson et al. 2015).
- **User feedback** and judgment of handling characteristics and other aspects.

Clinical Investigation Plan

CIP Reference No.:2018-GI (OEKG) -01. The **SAMISEN** study - Final Version 02 - Date 23th April 2019

- User feedback and assessment of handling characteristics and other logistical aspects regarding:
 - Handling of PowerSpiral
 - Instrument insertion of PowerSpiral
 - Precision of positioning during therapy of PowerSpiral
 - Time needed for procedure of PowerSpiral
 - Staff and resource needed for procedure of PowerSpiral

No hypothesis testing will be performed for any efficacy endpoint.

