2.4 Primary and secondary variables

Primary efficacy variable:

The rate of serious adverse events during and after enteroscopy will constitute the primary endpoint for this study.

Secondary efficacy variables:

- Reaching the anatomical region of interest: The rate of successfully reaching the suspected anatomical target region (either by antegrade or by retrograde route) compared to all attempts represents the endpoint 'anatomical success rate'.
- Therapeutic yield: Defined as the percentage of patients with any endoscopic intervention / therapy with the exception of biopsies. (Sethi et al. 2014; Prachayakul et al. 2013; Sanaka et al. 2012)
- Total procedure time: Period in minutes needed to complete the procedure.
- Total therapeutic intervention time: Period in minutes dedicated to therapeutic intervention(s).
- Total small bowel enteroscopy rate: Defined as complete evaluation of the small bowel either with a single approach or combined anterograde and retrograde approach (if complete small bowel enteroscopy is intended anyway (Committee et al. 2015; Gerson et al. 2015).
- Diagnostic Yield (i.e. diagnosis, that explains findings from previous imaging or establishes a new diagnosis, that could explain clinical symptoms, that indicated PSE)
- User feedback and judgment of handling characteristics and other aspects: User feedback and assessment of handling characteristics and other logistical aspects regarding:
 - Handling of PowerSpiral
 - Instrument insertion of PowerSpiral
 - Precision of positioning during therapy of PowerSpiral
 - Time needed for procedure of PowerSpiral
 - Staff and resource needed for procedure of PowerSpiral
- Serious adverse events (PS product related)
- Adverse events during enteroscopy procedure and adverse events (PS product related)

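### SAP 3.6 leaves the unit of the anatomical success rate undefined; counted over every procedure, it is not the share of patients reached and its interval ignores repeat attempts

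*SAP*

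**What the plan says.** SAP 3.6 defines the analysis: "The anatomical success rate (number of cases in which the suspected anatomical region is reached compared to all attempts) will be computed" with a 95% Clopper-Pearson interval, on the cITT population and, as a sensitivity analysis, on the ITT population. SAP 2.4 words the variable as "The rate of successfully reaching the suspected anatomical target region (either by antegrade or by retrograde route) compared to all attempts represents the endpoint" of anatomical success, and protocol 4.1.2 uses the same wording. None of the three places says what a case or an attempt is. The SAP sections that could hold a counting rule (3.4.2 for efficacy, 3.4.7 for other rules) both read None. The analysis populations in SAP 3.1 are made up of patients with at least one enteroscopy.

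On repeat procedures, protocol 3.1.2 says that "only part of the subjects will receive a second procedure", at the investigator's discretion and "usually because the region of interest could not be reached during the first endoscopy". Among the planned approaches in protocol 3.4.2 are starting by one route and adding the other if the first is unsuccessful or incomplete, and this one: "Perform a combined antegrade and retrograde examination during a single session".

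The word *case* appears in two other relevant places. Protocol 3.1.3 says "As main efficacy endpoint we will determine in how many cases the suspected anatomical target lesion can be reached". The sample-size row of the trial summary says the final dataset "will include 260 cases from procedure #6 onwards in order to account for a learning curve effect", where the 260 are the study subjects.

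**The concern.** The question in protocol 3.1.3, in how many cases the target can be reached, reads most naturally as a question about patients. A ratio over all attempts does not answer it once some patients have two attempts. Second attempts are mostly triggered by a failed first one, so the denominator depends on the outcome. A patient reached at the second procedure adds two attempts and one success.

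The Clopper-Pearson interval assumes a fixed number of independent trials. Here the number of attempts is random and depends on earlier results, and attempts within a patient may be related.

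Efficacy endpoints are not tested, so the estimate and its interval are the whole result. Two programmers could follow the SAP faithfully and report figures several points apart, with the choice made after the data are in.

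**Working it through.** **Plan figures.** The documents give no expected value, precision or second-procedure rate for this endpoint, so there is nothing of its own to reproduce. As a check on the interval method, exact limits from beta quantiles return all six rows of protocol Table 1, for example 20/245 = 8.2% (5.1% to 12.3%).

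**Notation.** Let p1 be first-attempt success, s the share of first failures that are retried, and p2 second-attempt success. All three are assumed. The number of evaluable patients, 245, comes from protocol 3.3.6. Second attempts are taken to follow only failures; the protocol says *usually*.

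- Second attempts per patient: q = (1 − p1) × s
- Per-patient rate: P = p1 + q × p2
- Rate over all attempts: R = (p1 + q × p2) / (1 + q) = P / (1 + q)

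Under this assumption no patient can succeed twice. The numerator is then the same whether a case is a patient or a procedure, and the denominator alone makes the difference.

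**Relative shortfall of R against P**, 1 − 1/(1 + q):

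- q = 0.05: 1 − 1/1.05 = 4.8%
- q = 0.10: 1 − 1/1.10 = 9.1%
- q = 0.20: 1 − 1/1.20 = 16.7%

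**Illustration with counts.** Take 245 patients, 196 reached at the first attempt, 25 of the 49 failures retried, and 12 of those reached.

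- Per patient: (196 + 12)/245 = 208/245 = 84.9% (79.8% to 89.1%)
- All attempts: 208/(245 + 25) = 208/270 = 77.0% (71.6% to 81.9%)
- First attempt only: 196/245 = 80.0% (74.4% to 84.8%)

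**Range and coverage.** The assumed grid was p1 = 60, 70, 80, 90%; s = 25, 50, 100%; p2 = 30, 50, 70%; with 40,000 simulated trials of 245 patients per scenario. Selected rows, in percent except q:

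| p1 | s | p2 | q | P | R | Gap (points) | All-attempts interval covers P | All-attempts interval covers R |
|---|---|---|---|---|---|---|---|---|
| 90 | 25 | 30 | 0.025 | 90.75 | 88.54 | 2.2 | 78.2 | 93.5 |
| 80 | 25 | 30 | 0.05 | 81.5 | 77.6 | 3.9 | 66.4 | 93.4 |
| 80 | 50 | 50 | 0.10 | 85.0 | 77.3 | 7.7 | 13.7 | 93.3 |
| 90 | 100 | 30 | 0.10 | 93.0 | 84.5 | 8.5 | 3.9 | 88.7 |
| 80 | 100 | 30 | 0.20 | 86.0 | 71.7 | 14.3 | 0.1 | 89.8 |
| 60 | 100 | 70 | 0.40 | 88.0 | 62.9 | 25.1 | 0.0 | 96.7 |

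Over the whole grid:

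- The gap runs from 2.2 to 25.1 points.
- The all-attempts interval covers P in 0% to 79% of trials, and R in 88.7% to 96.7%.
- When p1 = p2, R equals that common probability and coverage is 95.5% to 96.0%.
- Clopper-Pearson applied to the per-patient proportion covers P in 95.2% to 96.5%.

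The second and fifth rows differ only in the share retried. Retrying more patients raises the share reached from 81.5% to 86.0%, while the all-attempts figure falls from 77.6% to 71.7%. This reversal needs p2 below p1.

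**The case against.** A reader might go further and infer that the SAP divides patients by procedures, so that the rate is understated by a known amount and the interval is simply invalid. The documents do not support that.

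- **Unit.** SAP 3.6 says cases, not patients, although its next bullet (therapeutic yield) does say patients. Both words could mean procedures, or both could mean one per patient; on the latter reading the problem disappears. The trial summary leans towards patients but does not settle it.
- **Understated.** This holds only against the per-patient rate. R is a weighted mean of first- and second-attempt success, which is a legitimate quantity, and protocol 3.1.3 itself defines diagnostic yield per procedure. In the illustration R (77.0%) lies closer to first-attempt success (80.0%) than to the per-patient rate (84.9%).
- **Invalid.** As an interval for R, under-coverage is nil to moderate. The very low coverage appears only when the interval is read as describing patients.
- **Scheduling.** It is tempting to say that one combined session scores 1/1 while the same result over two days scores 1/2. No section says whether a combined session is one attempt or two, so this is a gap and not a demonstrated distortion.
- **Size and consequence.** Every gap rests on assumed rates. The SAP lists the endpoint as secondary, and no trial decision hangs on it.

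All of this limits the claim. It does not remove the need to fix the unit: no rule in the SAP chooses among these readings, and counting every procedure leaves the per-patient question unanswered.

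**Conclusion.** The point holds as a matter of an undefined unit with a real numerical consequence. If every procedure counts as an attempt and second attempts follow only failures, the planned ratio is the per-patient rate divided by (1 + q): about 9% lower in relative terms at q = 0.10 and 17% lower at q = 0.20. The documents do not give q, so the actual size is unknown. Read as a per-attempt rate, the figure is sound but different; its interval ignores within-patient dependence and under-covers slightly to moderately at worst. Read as the share of patients whose target was reached, the figure is too low and its interval is not valid. The change is worth making before analysis, but it touches a descriptive result only.

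**What to change.** In SAP 2.4 and 3.6:

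1. Define the anatomical success rate as the number of patients with the target region reached at V2 or V3, divided by all cITT patients, with the planned Clopper-Pearson interval. Repeat it on the ITT population as already foreseen.
2. Report first-procedure success beside it, one observation per patient.
3. If a per-attempt rate is kept, label it as such, state how a combined session counts, and use an interval that allows for clustering by patient.
4. Apply the same unit to the total small bowel enteroscopy rate in SAP 3.6. It also has an attempts denominator, and its definition allows a complete evaluation to be built from two routes.

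Align protocol 4.1.2 with the result.

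The cost is a wording change and one more table. The small-bowel segment reached and the route are already recorded at V2 and V3 (protocol 3.4.2), and scoring each attempt needs the same information, so no new data are required. Under protocol section 6, the change to 4.1.2 needs a written, approved amendment unless it counts as a minor administrative change. No hypothesis test is affected.

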3.8 Other Analyses

None.

3.9 *List of all tables / listings / figures with their location in Clinical Study Report*

DT = Descriptive statistics table with n, mean, standard deviation, median, 25th and 75th percentiles, minimum and maximum

FT = Frequency table with absolute and relative frequencies, for the primary endpoint, 95% confidence intervals will be added

GL = General listing of parameters with patient ID, center, analysis population in each listing.

Description of table / figure / listing	Type
Tables	
11.1.1 Patient Disposition - All Enrolled Population Reference: annCRF page 5 Parameters: Patients with entries Analyses: absolute and relative frequencies	FT
11.1.2 Analysis Populations - All Enrolled Population Reference: None Parameters: Analyses populations (SAF, cSAF, ITT, cITT) Analyses: absolute and relative frequencies	FT
11.1.3 In- and Exclusion criteria fulfilled? - SAF and cSAF Reference: annCRF page 5-6 Parameters: Categorical parameters Analyses: absolute and relative frequencies	FT
11.1.4 Visit Schedules - SAF and cSAF Reference: annCRF Page 3 Parameters: Median time from enrollment to discharge Analyses: Descriptive analyses	DT
11.1.5.1 Demographics and Baseline Characteristics - Continuous Parameters - SAF and cSAF Reference: SAP chapter 3.5 Parameters: Age Analyses: Descriptive analyses	DT
11.1.5.2 Demographics and Baseline Characteristics - Categorical Parameters - SAF and cSAF Reference: SAP chapter 3.5 Parameters: Sex Analyses: absolute and relative frequencies	FT
11.1.6 Previous Abdominal Surgery - SAF and cSAF Reference: annCRF page 10-11 Parameters: Previous abdominal surgery, etc. Analyses: absolute and relative frequencies	FT
11.1.7.1 Information About Small-Bowel Enteroscopy - Listing of Indication - SAF and cSAF Reference: annCRF page 12 Parameters: Indication Analyses: Listing of freetext	GL
11.1.7.2 Information About Small-Bowel Enteroscopy - SAF and cSAF Reference: annCRF page 12 Parameters: Categorical parameters on information about planned small-bowel enteroscopy Analyses: absolute and relative frequencies	FT

Description of table / figure / listing	Type
11.1.7.3 Initially Planned Procedure with PowerSpiral - SAF and cSAF Reference: annCRF page 12-13 Parameters: Categorical parameters Analyses: absolute and relative frequencies	FT
11.1.7.4 Initially Planned Procedure with PowerSpiral - Listing of Freetext - SAF and cSAF Reference: annCRF page 12-13 Parameters: Freetext Analyses: Listing of freetext	GL

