11.1.7.5 Procedure with PowerSpiral - Categorical Parameters - SAF and cSAF Reference: annCRF page 16-17 Parameters: Procedure with PowerSpiral, Procedural information Analyses: absolute and relative frequencies	FT
11.1.7.6 Procedure with PowerSpiral - Continuous Parameters - SAF and cSAF Reference: annCRF page 16-17 Parameters: Length of procedure, Time to reach deepest point of enteroscopy, Time score out Analyses: descriptive statistics	DT
11.1.7.7 Therapeutic Interventions - Listing of Comments - SAF and cSAF Reference: annCRF page 17 Parameters: Freetext, Start and Stop time of intervention by patient Analyses: Listing of freetext	GL
11.2.1 Assessment After Procedure - Categorical Parameters - ITT and cITT Reference: annCRF page 18 Parameters: Categorical parameters Analyses: absolute and relative frequencies	FT
11.2.2 Assessment After Procedure - Listing of Comments - ITT and cITT Reference: annCRF page 18 Parameters: Freetext Analyses: Listing of freetext	GL
11.2.3 Evaluation of Procedure - Categorical Parameters - ITT and cITT Reference: annCRF page 19-20 Parameters: Handling, instrument insertion, Precision, time needed, staff and resources needed Analyses: absolute and relative frequencies by category (worse, similar, better)	FT
11.2.4 Evaluation of Procedure - Diagnostic Yield - ITT and cITT Reference: SAP section 3.6 Parameters: positive imaging prior to procedure, information whether a diagnosis was made with PSE Analyses: absolute and relative frequencies	FT

Description of table / figure / listing	Type
11.3.1.1 Adverse Events during procedure - SAF and cSAF Reference: annCRF page 17 Parameters: Trigger question on AEs Analyses: absolute and relative frequencies	FT
11.3.1.2.1 Adverse Events by category - SAF and cSAF Reference: annCRF page 23 Parameters: Adverse event category Analyses: absolute and relative frequencies	FT
11.3.1.2.2 Serious Adverse Events by category - SAF and cSAF Reference: annCRF page 23 Parameters: Adverse event category Analyses: absolute and relative frequencies	FT
11.3.1.3 Adverse Events by category - Listing of other AEs - SAF and cSAF Reference: annCRF page 23 Parameters: Freetext Analyses: Listing of Freetext	GL
11.3.1.4.1 Adverse Events - Relatedness - SAF and cSAF Reference: annCRF page 23 Parameters: Relatedness Analyses: absolute and relative frequencies	FT

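### SAP 3.6 computes the total small bowel enteroscopy rate over all attempts instead of intended complete examinations, and does not define an attempt

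*SAP*

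**What the plan says.** SAP 2.4 describes the endpoint as follows: "Defined as complete evaluation of the small bowel either with a single approach or combined anterograde and retrograde approach". It then adds a condition in parentheses. The same condition stands in the protocol's trial summary and in protocol 3.1.3 and 4.1.2: "if complete small bowel enteroscopy is intended anyway".

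SAP 3.6, which tells the programmer what to compute, gives the rate as "number of complete evaluations of the small bowel divided by all attempts to reach the small bowel", with a 95% Clopper-Pearson interval. The condition is not repeated there.

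Other parts of the plan that bear on the point:

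- SAP 3.4.2, headed "Rules for efficacy", contains no rules.
- SAP 3.5 will report "Number of patients in whom a complete intervention was planned". It will also report patients by number of interventions and by complete or incomplete intervention. None of these counts is linked to the rate.
- No table in SAP 3.9 names the rate. The nearest are "11.1.7.3 Initially Planned Procedure with PowerSpiral - SAF and cSAF" and "11.2.1 Assessment After Procedure - Categorical Parameters - ITT and cITT", which are separate frequency tables.
- Protocol 3.4.2 records at V1 the answer to "Is a total enteroscopy of the small-bowel planned". At V2 and V3 it records whether total enteroscopy was achieved.
- Protocol 3.1.2 expects some, but not all, patients to have a second procedure.

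**The concern.** The rate is meant to show how often the device achieves a complete examination when one is sought. The registry takes any indication for deep enteroscopy, and V1 asks whether total enteroscopy is planned, so some patients will have a targeted examination only. Every enteroscopy in the study is an attempt to reach the small bowel. Read literally, SAP 3.6 counts the targeted examinations as failures to complete. The result then moves with the case mix as well as with the device's performance.

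The second problem is the unit. If an attempt is a procedure, a patient completed over V2 and V3 adds two to the denominator and one to the numerator. That does not fit a definition in which a combined approach is one evaluation. Two procedures in one patient are also not independent, as the Clopper-Pearson interval assumes. A combined examination in one session would naturally be a single attempt and raises no such problem.

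Two analysts following this SAP could report clearly different rates for the same endpoint, and the choice between them would be made with the data in hand.

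**Working it through.** **Plan's own figures.** The plan states no expected value or precision for this rate. The interval method can be checked on Table 1 of protocol 3.3.6: the exact limits for 20/245 are 5.1% to 12.3%, as printed, and the other five rows also agree.

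**Inputs.** From the documents: N = 245 analysable patients (protocol 3.3.6). Assumed, because the documents do not give them:

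- share with complete enteroscopy intended: 60%, so 0.60 × 245 = 147, leaving 98 not intended;
- completion among the intended: about 70%, so 103;
- second procedure in half of the intended: 74 additional procedures;
- completion among the 98 others: none, or 10.

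**Formulas.** Let I be the number intended, c the completions among them, e the completions among the others, and k the number of second procedures.

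- Rate by the definition: c / I
- SAP 3.6 per patient: (c + e) / N
- SAP 3.6 per procedure: (c + e) / (N + k)

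**Results with exact 95% intervals.**

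| Reading | No other completions | 10 other completions |
|---|---|---|
| Definition, c / I | 103/147 = 70.1% (62.0–77.3) | 103/147 = 70.1% (62.0–77.3) |
| SAP 3.6 per patient | 103/245 = 42.0% (35.8–48.5) | 113/245 = 46.1% (39.8–52.6) |
| SAP 3.6 per procedure, 245 + 74 = 319 | 103/319 = 32.3% (27.2–37.7) | 113/319 = 35.4% (30.2–40.9) |

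**Sensitivity to the intended share**, per patient, about 70% completion and no other completions:

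- 30% intended: 52/245 = 21.2%
- 90% intended: 154/245 = 62.9%
- 95% intended: 163/233 = 70.0% becomes 163/245 = 66.5% (60.2–72.4), an interval that still contains 70%
- 100% intended, no second procedures: 172/245 = 70.2%, unchanged

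**Effect of the unit alone.** If all 245 are intended and a quarter have a second procedure (61 more, 306 in total), the per-procedure rate is 172/306 = 56.2% (50.4–61.8), against 172/245 = 70.2% per patient.

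**Direction.** Without second procedures, the gap closes when patients not intended for complete enteroscopy are completed about as often as the others: 69 of 98 gives (103 + 69)/245 = 70.2%. It reverses above that: 78 of 98 gives (103 + 78)/245 = 73.9%. Understatement therefore requires that completion is less frequent where it was not intended, or that procedures are counted singly.

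**The case against.** The intent condition is a parenthesis. Neither SAP 2.4 nor the protocol names a denominator, and grammatically the parenthesis might qualify only the combined route. SAP 3.6 could be read as shorthand for the endpoint already defined in SAP 2.4, since it does not say that it replaces that definition. No passage says that V2 and V3 are separate attempts for this endpoint, and the wording on a single or combined approach points to one evaluation per patient. The counts and listings under SAP 3.5 would let a reader see planned status and completion. All magnitudes are assumed, and no test depends on the endpoint.

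Part of this stands. The per-procedure result is only one possible reading, the size cannot be known from the documents, and the endpoint is descriptive. The defect itself remains. Restricting the rate to intended cases is the natural meaning of a condition that the documents state four times. The phrase used in SAP 3.6 fits every examination in the registry and is not limited to attempts at total enteroscopy. The SAP 3.5 counts are marginal totals and do not supply the rate. The listings would allow it to be rebuilt, but a plan should not depend on the reader doing so.

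**Conclusion.** The concern holds. The rule in SAP 3.6 does not match the endpoint as defined in SAP 2.4 and in the protocol, and its unit of counting is undefined. Confidence is high for the mismatch. For its size there is only an assumed range: with completion near 70% in intended patients and no other completions, the per-patient rate runs from about 21% (30% intended) to about 67% (95% intended). It is unchanged if all patients are intended and procedures are not counted singly. The point should be corrected before analysis. It does not touch the primary serious adverse event conclusion, the sample size or any hypothesis test.

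**What to change.** In SAP 3.6, define the denominator as patients in the analysis population for whom total enteroscopy was planned at V1. Define the numerator as those of them in whom it was achieved, by a single approach or by V2 and V3 together. Use one record per patient and keep the Clopper-Pearson interval. Put this rule in SAP 3.4.2 and name in SAP 3.9 the table that will show the rate. A separate count of complete examinations in patients for whom none was planned would be a useful addition. The anatomical success rate can stay as the protocol defines it.

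The cost is SAP wording and table programming. Planned and achieved status are both already collected, so no new data and no change to study conduct are needed.
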